Diabetes Mellitus Aggravated	8.1	5.1
Pharyngitis	0.8	5.1

Rationale for the Selection of Dose and Schedule

We plan to prescribe pioglitazone 45 mg per mouth daily, which is the maximum U. S. Food and Drug Administration (FDA) approved dose for the treatment of type 2 diabetes mellitus. Pioglitazone has been extensively prescribed in humans at the planned doses for this study. The safety and toxicity profile of pioglitazone is well established. We do not expect a higher than usual toxicity in patients with pancreas cancer receiving pioglitazone.

IV. Schema

This is an open label, double arm Phase 2 study. We plan to enroll 15 patients with adenocarcinoma of the pancreas to this study of oral pioglitazone 45 mg daily. Patients are allowed to continue on antineoplastic therapy while on this study and this will be determined by the treating physician.

A control cohort of up to 10 patients will be enrolled for correlative (blood and radiological) testing alone. These patients will meet all criteria set forth for the study and follow the same study visits, but not be treated with pioglitazone.

V. Hypothesis

Prior studies have shown that a significant proportion of patients with metastatic pancreas cancer have metabolic changes consistent with insulin resistance. Treatment of insulin resistance in patients with metabolic disorders like type 2 diabetes mellitus is associated with improved outcomes and less morbidity. We propose an exploratory clinical trial to study as a primary aim, the effects of the oral inhibitor of the peroxisome proliferator- activated receptor gamma (PPAR γ) pioglitazone in markers of insulin resistance in patients with pancreas cancer.

Our primary hypothesis is that patients with pancreas cancer will have significant improvements in markers of insulin resistance when treated with pioglitazone.

As secondary aims, we will evaluate changes in cancer related symptoms, performance status, and weight. We will also evaluate the objective response of measurable lesions and the time to disease progression in patients with pancreas cancer. MRI will be used to assess for changes in body fat distribution and changes in intratumor fat content (UT Southwestern and PHHS patients ONLY). We will compare change in blood biomarkers and MRI between the pioglitazone and control arms.

VI. Objectives

Primary objective

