Cost Coverage: UT Southwestern Medical Center - Touchstone Diabetes Center is covering the costs of the pioglitazone for subjects enrolled onto this study. Invoices for reimbursement must be interoffice mailed to [name] at mail code 8549. (Mailing Address: UT Southwestern Medical Center at Dallas, Touchstone Diabetes Center, [name], [name], [name] Attn: [name])

Dispensation: Each subject should be given a one month (28-day) supply of pioglitazone per cycle.

Accountability: The investigator and investigator site are responsible for maintaining an accurate inventory and accountability logs for the study drug, pioglitazone, for patients enrolled on this study. The site is permitted to use their own drug accountability form to record study drug dispensation and patient returned tablets. These forms should be stored in the site's dispensing pharmacy. Use of standard pharmacy accountability logs is acceptable.

2. Administration schedule:

Patients will be instructed to take pioglitazone (45mg daily by mouth) and will be instructed on how to take the pioglitazone for the entire cycle (one cycle equals 28 days). Subjects will continue taking pioglitazone daily for two cycles (no more than 8 weeks) or until one of the following criteria mentioned in section XIII D. Subjects will record their daily drug administration on a dosing diary, supplied by the study coordinator, in order to verify subject dosing compliance.

See table below for treatment schedule (cycle one and subsequent cycles)

Study Drug	Cycle 1				Cycle 2			
	Week 1	Week 2	Week 3	Week 4	Week 5	Week 6	Week 7	Week 8
Pioglitazone	daily	daily	daily	daily	daily	daily	daily	daily

D. Dose Modifications and Discontinuation

- Patients developing a treatment-related CTCAE v4 Grade 1 or 2 adverse event will have their dose continued at the same level.
- Pioglitazone must be held for any grade 3 or 4 toxicity until the event resolves to at least grade 2. Following the resolution, the dose of pioglitazone must be reduced to level -1.
- The following table describes potential dose level modifications for pioglitazone. If a subject requires a dose reduction is beyond level -2, pioglitazone must be discontinued.
- Patients removed from treatment for intolerable toxicity must be followed for evaluation of their time to disease progression (TDP).

Agent	Initial Dose	Level -1	Level -2
Pioglitazone	45 mg /day	30 mg/day	15 mg/day

For all toxicities:

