Standard symptomatic treatment will be offered by the treating physician. There is no dose modification of pioglitazone for grade 1 or grade 2 toxicity

Interruption in pioglitazone for greater than 14 days is not allowed. Subjects must discontinue treatment if this occurs.

- Hematologic Toxicities
There is no need to modify or discontinue pioglitazone due to hematologic toxicity.
- Diarrhea
For grade 3 or 4 diarrhea, hold pioglitazone until diarrhea resolves to ≤ grade 2, then it may be resumed at one lower dose level.
- Nausea and Vomiting
For grade 3 or 4 nausea or vomiting, hold pioglitazone until nausea and vomiting resolve to ≤ grade 2,

then it may be resumed at one lower dose level.

- Liver Function Tests

For grade 3 or 4 elevation of the liver function tests, hold pioglitazone until elevation of the liver function tests resolve to \leq grade 2, then gemcitabine and pioglitazone may be resumed at one lower dose level.

- Weight Gain

For grade 3 or 4 weight gain, hold pioglitazone until peripheral edema resolves to grade 2, then it may be resumed at one lower dose level.

E: Concomitant medication/Treatments:

Pioglitazone is metabolized through the cytochrome P450 2C8/9 and 3A4 pathways. The metabolic pathway of concomitant medications will be checked prior to prescribing with pioglitazone. According to the pioglitazone prescribing information, co administration of pioglitazone and gemfibrozil, a strong CYP2C8 inhibitor, increases pioglitazone exposure approximately 3-fold. Therefore, the maximum recommended dose of pioglitazone is 15 mg daily when used in combination with gemfibrozil or other strong CYP2C8 inhibitors.

Other strong CYP2C8 inhibitors include fluconazole, ketoconazole, nocardipine, sulfonamides, and some NSAIDs. Concomitant medications that are inhibitors of CYP 3A4 are likely to increase pioglitazone exposure as well and CYP 3A4 inducers may decrease pioglitazone concentrations.

Concomitant administration of pioglitazone with thioridazine is contraindicated

F. **Treatment Evaluations**

Same procedure will be followed for pioglitazone (treatment) and control arms except the control arm will not receive study drug (pioglitazone) and therefore will not have a pill diary

2-week visit (+/- 7 days)

- Symptom Driven Physical Examination (PE)
- Vital Signs - BP, HR, RR, and Temp ($^{\circ}$ C)
- Weight (kg, record on weight log)
- ECOG performance status
- AE/Toxicity assessment
- Laboratory assessments:

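### The dose-modification rules in Section XIII.D cannot all be followed as written: haematologic events, later events and the gemcitabine clause need reconciling

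*Combined protocol and SAP*

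**What the plan says.** All the dose rules are in Section XIII.D of the combined protocol and SAP, with related text in Sections IV and XIV.

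- **General rule.** "Pioglitazone must be held for any grade 3 or 4 toxicity until the event resolves to at least grade 2". Then: "Following the resolution, the dose of pioglitazone must be reduced to level -1". The bullet just before it, on grade 1-2 events, is restricted to treatment-related events. This one is not.
- **Dose table and floor.** Pioglitazone only: 45 mg/day at the start, 30 mg/day at level -1, 15 mg/day at level -2. "If a subject requires a dose reduction is beyond level -2, pioglitazone must be discontinued". Section XIV, item 6, ends treatment for a patient who needs a third reduction.
- **Interruption limit.** A gap in pioglitazone of more than 14 days ends treatment (XIII.D, and XIV item 7).
- **Haematologic toxicity.** "There is no need to modify or discontinue pioglitazone due to hematologic toxicity". No grade is mentioned.
- **Diarrhoea, nausea and vomiting, weight gain.** Hold at grade 3 or 4, "then it may be resumed at one lower dose level".
- **Liver function tests.** Hold pioglitazone at grade 3 or 4 until recovery, "then gemcitabine and pioglitazone may be resumed at one lower dose level".
- **Chemotherapy.** Section IV: "Patients are allowed to continue on antineoplastic therapy while on this study and this will be determined by the treating physician".

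Nothing in these sections says which rule prevails when the general and the event-specific text differ.

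**The concern.** A site applying XIII.D has to choose between instructions that lead to different doses. The haematologic case is foreseeable: chemotherapy may continue on study, a planned new regimen must have begun no more than 21 days before enrolment (Section IX), and blood counts are taken at weeks 2, 4, 6 and 8 (XIII.F). For a severe low count, one rule holds and reduces the drug and, if the hold exceeds 14 days, ends treatment. The other leaves dosing alone.

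The statistical stake is exposure. The primary endpoint is change in insulin-resistance markers after 8 weeks of pioglitazone in 15 treated patients. If dose and duration depend on which sentence a site follows, what was given becomes harder to describe and dose-modification data harder to interpret. There is a safety side too, because these rules are meant to tell the treating physician what to do.

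**Working it through.** The plan gives no figure on this point. The check sets the rules side by side and traces the pioglitazone dose from the protocol's own table (45, 30, 15 mg/day).

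**Dose after a grade 3-4 event, once it has resolved**

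| Situation | General rule, read literally | Event-specific rule |
|---|---|---|
| First listed non-haematologic event, at 45 | 30 (mandatory) | 30 (permitted) |
| Second listed non-haematologic event, at 30 | 30, so no reduction | 15 |
| Further listed event, at 15 | 30, which is not a reduction | Below level -2, so discontinue |
| Haematologic event, at 45 | Hold, then 30 | No change, 45 continues |
| Second event of a type not listed, at 30 | 30, so no reduction | None exists |

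**1. Haematologic toxicity.** The general rule covers every grade 3-4 toxicity and uses *must*. The haematologic bullet covers every grade and says no change is needed. A grade 3-4 blood toxicity falls under both, and both cannot be followed.

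**2. Relatedness.** The grade 1-2 bullet names treatment-related events; the grade 3-4 bullet does not. Read literally, a severe event due to chemotherapy or to the cancer also triggers the hold. For events without a specific rule, no other text settles this.

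**3. Later events.** The general rule names a fixed target ("the dose of pioglitazone must be reduced to level -1"). The event-specific rules name a relative step. For a first event the target level is the same and only *must* versus *may* differs. From the second event on they diverge, as the table shows. The level -2 column, the rule for going below it and the third-reduction criterion in Section XIV all presuppose a second step that the general sentence does not supply.

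**4. Gemcitabine.** This is a separate defect. The liver-function rule holds only pioglitazone but resumes two drugs. The dose table has no gemcitabine row, so a lower level of it has no meaning here. Section IV leaves antineoplastic therapy to the treating physician.

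**The case against.** The strongest reply is that a sensible reader can resolve most of this.

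- **Haematologic events.** Grade 1-2 events already need no dose change, so the haematologic bullet adds something only if it is an exception for grade 3-4. That is the natural reading. But precedence is never stated, and a permissive phrase is set against a *must*.
- **Later events.** A reader might infer that the plan allows no second reduction. The documents do not support that: the level -2 column, the rule below it and Section XIV, item 6, show that stepwise reduction is intended. What remains is that the general sentence does not say so, and it is the only rule for unlisted toxicities.
- **Gemcitabine.** A reader might infer that the general rule contradicts the liver rule on gemcitabine, or that chemotherapy is altered in the treated arm only. Neither follows. The general rule is silent on gemcitabine, and the clause says *may*, so it orders no change. The conflict is with Section IV and the pioglitazone-only table.
- **Power.** A reader might infer that patients stopped after a long haematologic hold are lost and that power falls. With the Section XX inputs (mean change 0.4, SD 0.5, two-sided 0.05, one-sample t-test), the stated 82% reproduces as 82.1% at n = 15; it would be 75.4% at n = 13 and 71.4% at n = 12. That loss is not supported. The documents give no rate of such events, so losing 2 or 3 patients would be pure assumption. The early-termination visit in XIII.F collects adiponectin, glucose tolerance and insulin from anyone who stops before 8 weeks, and nothing excludes those patients from the analysis.

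**Conclusion.** The point holds as an internal inconsistency in XIII.D. Two conflicts lie between the general and the event-specific rules: haematologic toxicity, and the dose step after a later event. One ambiguity concerns whether unrelated grade 3-4 events trigger the hold. One stray clause, on gemcitabine, conflicts with Section IV and with the dose table.

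In dose terms, the readings differ by 30 versus 45 mg/day after a resolved haematologic event and by 30 versus 15 mg/day after a second listed event. A haematologic hold lasting more than 14 days would end treatment under one reading and never begin under the other. These contrasts rest only on the literal wording and the protocol's own table. How many patients would be affected cannot be estimated from the documents, and no effect on power is claimed. The consequence is inconsistent handling of the same toxicity and inconsistent study-drug exposure. It should be corrected because it bears on safety instructions and is easy to put right. Which rule is clinically correct is not a matter for this review.

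**What to change.** Amend the wording of XIII.D so that its rules agree with each other and with Sections IV and XIV. The amendment should state:

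1. which rule takes precedence for haematologic events, and at which grades;
2. whether the grade 3-4 hold applies to all events or only to related ones;
3. how dose steps apply to second and later events, including toxicities with no specific rule, and whether the reduction is mandatory or permitted;
4. for the liver-function rule, either no mention of gemcitabine or wording consistent with Section IV.

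The clinical team decides the content of each. The cost is one wording amendment, with no added visits, procedures or sample size.

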1. Describe change in markers of insulin resistance, including in adiponectin levels standard glucose tolerance test, and serum levels of insulin and glucose in patients with pancreas cancer receiving pioglitazone.

Secondary Objectives

1. To determine the tumor response by RECIST in patients with pancreas cancer receiving pioglitazone.
2. To describe changes in weight in patients with pancreas cancer receiving pioglitazone.
3. To describe changes in ECOG performance status in patients with pancreas cancer receiving pioglitazone.

4. To describe changes in symptoms and quality of life using the FACT-Hep scale, version 4 (see Appendix 4).
5. Compare change in blood biomarkers and MRI between the pioglitazone and control arms.

VII. Endpoints

We will assess the primary and secondary endpoints of the study as follows:

Primary End point

The primary end point will be improvement in insulin resistance markers:

- a. Change in serum adiponectin level. We will obtain serum levels of adiponectin at baseline and after 8 weeks of treatment with pioglitazone.
- b. Changes in standard glucose tolerance test. We will perform the area under the oral glucose tolerance test at baseline and after 8 weeks of treatment with pioglitazone.
- c. Fasting levels of serum glucose and insulin. We will obtain serum levels of fasting glucose and insulin every four weeks in all patients receiving pioglitazone

Secondary End points

- a. Objective response (OR) is the proportion of patients with confirmed complete response (CR) or confirmed partial response (PR) according to the Response Evaluation Criteria in Solid Tumors (RECIST). Progression free survival (PFS) and overall survival (OS) of patients on treatment with pioglitazone.
- b. Changes in weight in patients with pancreas cancer receiving pioglitazone.
- c. Changes in ECOG performance status in patients with pancreas cancer receiving pioglitazone.
- d. Changes in symptoms and quality of life using the FACT-Hep questionnaire, version 4 (see Appendix 4).
- e. Characterize MRI determined changes in a) pancreatic intratumor fat; and b) body fat distribution in pancreatic cancer patients treated with pioglitazone (pilot study on 8-10 patients chosen by PI/investigator discretion) (UT Southwestern and PHS patients ONLY).
- f. Compare changes in serum and MRI end points between pioglitazone and control arms.

VIII. Study Design

Study Arm:

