We plan to enroll fifteen patients with metastatic or locally advanced pancreas cancer into a double arm pilot exploratory study of oral pioglitazone 45 mg daily.

Treatment will be administered for 8 weeks and then stopped.

Control Arm:

Up to ten patients meeting eligibility criteria will be enrolled in the control arm. Patients will be treated per standard of care treatment at the discretion of the treating team and will not be treated with pioglitazone.

Treatment arm assignment:

Treatment arm will be assigned by the principal investigator or treating MD at their discretion. Given the exploratory nature of this study, randomization will not be performed.

Control arm patients can include the following examples:

- patient declines pioglitazone therapy but agrees to biomarker testing (Adiponectin, a hormone made by fat cells, will be measured). Additional assays may be performed
- Patient is enrolled in another clinical trial which does not allow experimental therapy (pioglitazone) to be given. The protocol of the patient's study will be reviewed to ensure biomarker testing (Adiponectin, a hormone made by fat cells, will be measured) as defined in this study is not specifically prohibited.

- Patients enrolled after completion of the 15 study arm patients
- Other patients as deemed appropriate by the PI or co-Is

A. Recruitment

Eligible study patients will be screened, recruited, and enrolled at the following institutions:

1. University of Texas Southwestern Medical Center at Dallas:
 - a. Harold C. Simmons Comprehensive Cancer Center
 - b. University Hospital – Zale Lipshy
 - c. University Hospital – Saint Paul
2. Parkland Health and Hospital System (PHHS)
3. VA North Texas (Dallas)

Study patients will be recruited from the practices of the PI and co- investigators. Potentially eligible patients will be approached by their health care providers who can refer them to the study coordinator for screening. All patients being considered for the study and eligible must sign an informed consent for the study prior to any study specific procedures.

IX. Eligibility Criteria

Inclusion Criteria

Inclusion Criteria	Reason
Signed informed consent	Document patient participation and understanding of study requirements
Histologically proven adenocarcinoma of the pancreas	Disease of interest
Radiologically measurable disease	Target lesion to follow response to therapy

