 - b. CT scan of abdomen and pelvis with IV and PO contrastFollowing completion of the pretreatment assessments and confirmation of eligibility, patients will be registered, assign a subject identification number, evaluated and followed up according to the study procedures described below. Since this is a double arm, pilot study,

randomization to different treatment arms is not required.

B. Week 0 (**Baseline evaluation**)

The following baseline evaluations assessment will be performed on cycle 1 day 1 prior to the first dose of study drug: Control arm patients will have the same evaluation but will not receive study drug)

- Complete Physical Examination (PE)
- Vital Signs - BP, HR, RR, and Temp (°C)
- Weight (kg, record on weight log)
- ECOG Performance Status
- AE/Toxicity Assessment
- Laboratory assessments:
 - Hematology: CBC with differential and platelet count
 - Serum chemistry: Na, K, Cl, Ca, bicarbonate, BUN, creatinine, AST, ALT, alkaline phosphatase, total bilirubin, total protein, albumin
 - Pregnancy test (WOCBP ONLY)
 - CA19-9
 - C-reactive protein level
 - Serum fasting glucose (fasting for at least 8 hours)
- Exploratory Research Lab Evaluations
 - Glucose tolerance test (0 baseline and 2 hr ingestion)
 - Insulin level (0 hr baseline and 2 hr post ingestion)
 - Adiponectin (0 hr baseline)

 - MCP-1 level (0 hr baseline)
- FACT-Hep Questionnaire

- MRI abdomen noncontrast (Research) Should be done +/- 7 days of starting pioglitazone (7 days pre or 7 days after starting pioglitazone) MRI will be done on 8-10 patients chosen at PI/investigator discretion (UT Southwestern and PHS patients ONLY).

C. **Treatment Plan**

1. **Prescription Information**

How Supplied: Pioglitazone is available in 15 mg, 30 mg, and 45 mg tablets. The 15 mg tablets are white to off-white, round, convex, non-scored tablets with "ACTOS" on one side and "15" on the other side. The 30 mg and 45 mg tablets are white to off white, round, flat, non-scored tablets with "ACTOS" on one side and "30" or "45" (respectively) on the other side. Availability: Each (15 mg, 30 mg and 45 mg) are available in bottles of 30, 90 or 500.

Storage: Pioglitazone should be stored at 25 °C (77°F); excursions permitted to 15-30°C (59-86°F). Keep the container closed tightly, and protect from moisture and humidity.

Ordering: The investigational drug pharmacist will purchase a bulk (cost efficient) supply of pioglitazone and dispense to study participants.

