 - Hematology: CBC with differential and platelet count
 - Serum chemistry: Na, K, Cl, Ca, bicarbonate, BUN, creatinine, AST, ALT, alkaline phosphatase, total bilirubin, total protein, albumin
 - C-reactive protein level
 - Serum fasting glucose (fasting for at least 8 hours)
- Exploratory Research Lab Evaluations
 - Insulin level (0 hr baseline)
 - Adiponectin (0 hr baseline)

 - MCP-1 level (0 hr baseline)

4 Week Visit (+/- 7 days)

- Symptom Driven Physical Examination (PE)
- Vital Signs - BP, HR, RR, and Temp ($^{\circ}$ C)
- Weight (kg, record on weight log)
- ECOG Performance Status
- AE/Toxicity assessment

- Laboratory assessments:
 - Hematology: CBC with differential and platelet count
 - Serum chemistry: Na, K, Cl, Ca, bicarbonate, BUN, creatinine, AST, ALT, alkaline phosphatase, total bilirubin, total protein, albumin
 - CA19-9
 - C-reactive protein level
 - Serum fasting glucose (fasting for at least 8 hours)
- Exploratory Research Lab Evaluations
 - Glucose tolerance test (0 baseline and 2 hr post ingestion)
 - Insulin level (0 hr baseline and 2 hr post ingestion)
 - Adiponectin (0 hr baseline)
 - MCP-1 level (0 hr baseline)
- FACT-Hep Questionnaire
- Review of Patient Pill Diary
- Patient will receive 4 week refill of Pioglitazone

6-week visit (+/- 7 days)

- Symptom Driven Physical Examination (PE)
- Vital Signs - BP, HR, RR, and Temp (°C)
- Weight (kg, record on weight log)
- ECOG Performance Status
- AE/Toxicity assessment
- Laboratory assessments:
 - Hematology: CBC with differential and platelet count
 - Serum chemistry: Na, K, Cl, Ca, bicarbonate, BUN, creatinine, AST, ALT, alkaline phosphatase, total bilirubin, total protein, Albumin
 - C-reactive protein level
 - Serum fasting glucose (fasting for at least 8 hours)
- Exploratory Research Lab Evaluations
 - Insulin level (0 hr baseline)
 - Adiponectin (0 hr baseline)
 - MCP-1 level (0 hr baseline)

8 week visit (+/- 7 days)

- Symptom Physical Examination (PE)
- Vital Signs - BP, HR, RR, and Temp (°C)
- Weight measurement (kg, record on weight log)
- ECOG performance status
- AE/Toxicity Assessment
- Laboratory assessments:
 - Hematology: CBC with differential and platelet count
 - Serum chemistry: Na, K, Cl, Ca, bicarbonate, BUN, creatinine, AST, ALT, alkaline phosphatase, total bilirubin, total protein, albumin
 - CA19-9
 - C-reactive protein level
 - Serum fasting glucose (fasting for at least 8 hours)
- Exploratory Research Lab Evaluations

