 - Glucose tolerance test (0 hr baseline and 2 hr post ingestion)
 - Insulin level (0 hr baseline and 2 hr post ingestion)
 - Adiponectin (0 hr baseline)

- MCP-1 level (0 hr baseline)
- FACT-Hep Questionnaire
- Disease Assessment
- Chest x-ray or CT scan of the chest
- CT scan of the abdomen and pelvis
- Review of Patient Pill Diary
- MRI Abdomen non-contrast (research study) (UT Southwestern and PHHS patients ONLY)

Early-Term or End of treatment visit (ET/EOT) (Early-Term, if patient discontinues treatment before 8 weeks for any reason) (+/-7 days)

- Complete physical examination
- Vital Signs - BP, HR, RR, and Temp (°C)
- Weight (kg on weight log)
- ECOG Performance Status e
- AE/Toxicity assessment
- Laboratory assessments:
 - Hematology: CBC with differential and platelet count
 - Serum chemistry: Na, K, Cl, Ca, bicarbonate, BUN, creatinine, AST, ALT, alkaline phosphatase, total bilirubin, total protein, albumin
 - CA19-9
 - C-reactive protein level
 - Serum fasting glucose (fasting for at least 8 hours)
- Exploratory Research Lab Evaluations
 - Glucose tolerance test (0 hr baseline and 2 hr post ingestion)
 - Insulin level (0 hr baseline and 2 hr post ingestion)
 - Adiponectin (0 hr baseline)
 - MCP-1 level (0 hr baseline)
- FACT-Hep Questionnaire
- MRI Abdomen non-contrast (research study) (UT Southwestern and PHHS patients ONLY)

Follow up (2 weeks after completing treatment or last treatment date if Early-term (ET)) (+/- 7 days) (this corresponds to week 10 of control arm patients)

- Complete physical examination
- Vital Signs - BP, HR, RR, and Temp (°C)
- Weight (kg, record on weight log)
- ECOG Performance Status
- Laboratory assessments:
 - Hematology: CBC with differential and platelet count
 - Serum chemistry: Na, K, Cl, Ca, bicarbonate, BUN, creatinine, AST, ALT, alkaline phosphatase, total bilirubin, total protein, albumin
 - CA19-9
 - C-reactive protein level
 - Serum fasting glucose (fasting for at least 8 hours)
- Exploratory Research Lab Evaluations
 - Glucose tolerance test (0 hr baseline and 2 hr post ingestion)
 - Insulin level (0 hr baseline and 2 hr post ingestion)
 - Adiponectin (0 hr baseline)
 - MCP-1 level (0 hr baseline)
- FACT-Hep Questionnaire

- Toxicity/AE assessment

Long term Follow-up

Patient's chart will be reviewed intermittently by the study team to assess:

- Disease status
- Vital status

G. *Imaging Procedures*

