 - **PAI-1** performed at the MagPix multiplexing matching housed at the UT Southwestern Metabolic Core [2]
- Prior to shipment, complete the sample inventory logs for each patient so that specimen chain of custody can be established. Include in each batch shipment copies of; 1) the blood collection source documents for each patient; and 2) copies of each subjects specimen inventory form. Keep originals of these documents in the patient chart. Please see appendix XX, Specimen Processing and Shipment Instructions for further details.

Patients accrued at VA North Texas will have sample collected at the respective sites, frozen at -20 to -80 C and shipped on dry ice in batches to the UTSW Metabolic Core via overnight courier FedEx (FedEx number:370843180) to the following address

[name] Laboratory
 Touchstone Diabetes Center
 Department of Internal Medicine
 The University of Texas Southwestern Medical Center
 [name]
 [name]
 [name]
 [contact]
 [contact]

H. Schedule of Events

Procedures	Screening ¹	Baseline	2-Weeks	4-weeks	6-Weeks	8-Weeks	End of Treatment or Early-Term (EOT/ET)	14 –Day Follow-up ³
Informed Consent	X							
I/E & Medical History	X							
Concomitant Medications Review / AE Assessment	X	X	X	X	X	X		
Physical Exam	X		X	X	X	X	X	X
Height (cm) ² and Weight Measurement (Kg)	X		X	X	X	X	X	X
Performance status (ECOG)	X	X	X	X	X	X	X	X
Hematology ⁴		X	X	X	X	X	X	X
Serum Chemistry ⁵		X	X	X	X	X	X	X
Serum pregnancy test	X	X						
CA 19-9		X		X		X	X	X
C-reactive protein		X	X	X	X	X	X	X
Serum fasting glucose		X		X		X	X	X
Glucose tolerance		X		X		X	X	X
Adiponectin		X	X	X	X	X	X	X
Insulin level		X ⁶	X	X ⁶	X	X ⁶	X	X
2 hour insulin level		X		X		X	X	X
MCP-1		X	X	X	X	X	X	X
Chest x-ray or Chest CT scan	X					X	X ⁷	X
CT scan of abdomen and pelvis	X					X	X ⁷	X
Toxicity Assessment		X	X	X	X	X	X	
FACT-Hep Questionnaire		X		X		X	X	X
MRI abdomen noncontrast		X ⁸					X ¹⁰	

1. Within 28 days before starting pioglitazone/Day 1 for control arm
2. Height performed at screening only
3. Within 14 days after discontinuing pioglitazone/week 8 for control arm

4. Hematology: CBC with differential and platelet count
5. Serum chemistry: Na, K, Cl, Ca, bicarbonate, BUN, creatinine, AST, ALT, alkaline phosphatase, total bilirubin, total protein, albumin
6. To be performed in conjunction with glucose tolerance test at 0 hr baseline and 2 hr post ingestion.
7. Chest x-ray must be posterior to anterior (PA) and lateral (LAT) plain chest x-ray.

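### The week-8 window lets the primary blood samples fall up to about 7 days after the last dose, and the baseline MRI may follow up to 7 days of dosing; tightening both is a cheap improvement

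*Combined protocol and SAP*

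**What the plan says.** **Dosing.** The baseline evaluation, including the blood draw, "will be performed on cycle 1 day 1 prior to the first dose of study drug" (XIII.B). Section VIII says "Treatment will be administered for 8 weeks and then stopped", and XIII.C.2 says "Subjects will continue taking pioglitazone daily for two cycles (no more than 8 weeks".

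**Primary samples.** Section VII says "We will obtain serum levels of adiponectin at baseline and after 8 weeks of treatment with pioglitazone" and times the glucose tolerance test in the same way. The visit that delivers these samples is listed in XIII.F as "8 week visit (+/- 7 days". XX.A defines x_1 only as the adiponectin level after treatment. None of these places limits the number of days since the last dose.

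**Early stopping.** A separate visit with the same blood panel is headed "Early-Term, if patient discontinues treatment before 8 weeks for any reason) (+/-7 days".

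**Follow-up.** XIII.F has "Follow up (2 weeks after completing treatment or last treatment date if Early-term (ET)) (+/- 7 days". Footnote 3 of the Schedule of Events has "Within 14 days after discontinuing pioglitazone/week 8 for control arm".

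**MRI.** XIII.B, XIII.G and the Schedule of Events footnotes allow the baseline scan up to 7 days after the first dose and the second scan up to 14 days after the last.

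**Analysis.** XX.B plans graphs over time, mean and median changes, and a dichotomised improvement rate. It does not use time since last dose. MRI and between-arm comparisons are labelled exploratory.

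**The concern.** The trial asks what pioglitazone does to insulin-resistance markers, so the post value should reflect a patient on the drug and the pre value a patient not yet on it. The windows allow a compliant site to breach both conditions: a week-8 sample taken several days after dosing has ended, and a baseline MRI taken when the Pharmacokinetics paragraph already puts the drug at steady state (within 7 days). If the effect fades after stopping, or has begun before the MRI, the measured change is too small. With 15 treated patients there is little room for avoidable dilution. The blood samples matter more than the MRI, because they carry the primary endpoint.

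**Working it through.** **1. The plan's own figure.** Inputs from XX.A: n = 15, mean change 0.4, SD 0.5, significance level 0.05. Sidedness is not stated. A two-sided one-sample t test has noncentrality 0.4/0.5 × √15 = 3.098 on 14 degrees of freedom, which gives power of 82.1%. The stated 82% reproduces.

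**2. Day count, assuming uninterrupted dosing.** Two cycles of 28 days from day 1 put the last dose on day 56.
- Week-8 visit: 56 ± 7 = days 49 to 63, which is 15 days.
- Day 57 is an ordinary 24-hour trough under once-daily dosing.
- Days 58 to 63 are 2 to 7 days after the last dose: 6 of 15 = 40% of the permitted days.

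**3. Follow-up window on the same count.**
- XIII.F: (56 + 14) ± 7 = days 63 to 77.
- Footnote 3: days 57 to 70.

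The first meets the week-8 window only on day 63. The second covers its whole late half, days 57 to 63.

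**4. Drug level.** The half-life of total pioglitazone is 16 to 24 hours (Pharmacokinetics). Seven days (168 h) after the last dose, relative to the 24-hour trough:
- 2^(−(168 − 24)/16) = 0.2%
- 2^(−(168 − 24)/24) = 1.6%

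This is drug level, not biomarker effect.

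**5. Illustration of fading.** The halving times and attendance patterns are assumptions; the documents give neither. The effect is full up to day 57 and then 2^(−(day − 57)/h) of full. Mean change is 0.4 × the average retained fraction.

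| Halving time h (days) | Mean change, uniform attendance | Power, SD fixed at 0.5 | Power, spread shrinks with effect | Power, SD 0.5, attendance peaking at day 56 |
|---|---|---|---|---|
| no fading | 0.400 | 82% | 82% | 82% |
| 28 | 0.387 | 80% | 82% | 81% |
| 14 | 0.375 | 77% | 82% | 79% |
| 7 | 0.355 | 72% | 81% | 76% |
| 3 | 0.317 | 63% | 77% | 70% |

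The fourth column is by simulation, 200,000 runs per row with fading. The last column uses triangular weights over days 49 to 63, under which 33% of samples are late.

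**6. MRI.** With a baseline scan after 7 days of dosing, a completer has 56 − 7 = 49 of 56 dosing days between scans (87.5%). A patient stopping at 6 weeks has 35 of 42 (83%). These are shares of exposure at the extreme edge of the window, not estimates of bias.

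**The case against.** The strongest reply is that the harm rests on a quantity the documents do not supply. A ±7-day window is ordinary, it is applied alike at weeks 2, 4, 6 and 8, and this is a pilot whose primary objective is descriptive. That stands, and it limits the claim to a possible dilution. A visible loss of power in the table needs both fast fading and an unchanged SD.

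The day-56 anchor is also conditional. The second 28-day supply is given at a week-4 visit that is itself ±7 days, so a late refill can shift dosing and shorten the gap. Holds of up to 14 days (XIII.D) can lengthen it. This stands too, and it is a reason to derive the actual interval.

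Much of the safeguard is already collected: adiponectin and insulin at weeks 2, 4 and 6, a glucose tolerance test at week 4, dated and visit-labelled samples, a daily pill diary and plots over time. What is missing is a stated use of these data for this purpose. The check is thinnest for the glucose tolerance test, with one other on-drug point.

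Three stronger readings are tempting, and the documents do not support them:
- **A reader might infer that early-termination or end-of-treatment samples are off-drug primary samples.** Section VII ties adiponectin and the glucose tolerance test to 8 weeks of treatment, and nothing makes the other visit's sample x_1. Using it as x_1 in the main analysis would add values after short exposure.
- **A reader might infer that the follow-up conflict contaminates the primary endpoint.** Samples are labelled by visit, and the column heading, the week-10 remark for controls and the weight log all point to two weeks. It is a wording conflict to reconcile.
- **A reader might infer from the half-life that the effect has gone by day 63.** The half-life describes drug, not adiponectin or glucose response.

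**Conclusion.** The point holds as a cheap improvement. With uninterrupted dosing, a compliant week-8 blood sample can be 2 to 7 days after the last dose on 6 of 15 permitted days, and a baseline MRI can follow up to 7 days of dosing. Fading, or an early effect before the MRI, could only shrink the measured change. By how much is unknown, and the answer may be none. The table is a range under assumed inputs, not an estimate for this trial. It would be wrong to conclude that the trial is underpowered or that 82% is in error. The MRI part is secondary: exploratory, and in 8 to 10 patients.

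**What to change.** 1. **Week-8 blood draw.** Make the window one-sided, for example −7/+1 days around the last planned dose, as a scheduling aim. Late samples are still collected and stay in the main analysis.
2. **Baseline MRI.** Take it before the first dose.
3. **Days since last dose.** Derive it in whole days from the collection date (XIII.H) and the pill diary (Appendix 3), and report it. Whole days are the limit, because the diary records date and yes/no but not the time of the dose. Add one supportive sensitivity analysis restricted to week-8 samples drawn no later than the calendar day after the last dose.
4. **Follow-up window.** Reconcile XIII.F with footnote 3 of the Schedule of Events.

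**Cost.** Window wording, one derived variable, one extra analysis, and somewhat tighter scheduling of a fasting visit in ill patients and of 8 to 10 scans. The Background reports that adequate follow-up was not possible in a previous study, which is why the +1 day is an aim and not a rule for discarding data. An early draw on day 49 is on drug but has about a week less exposure. The sensitivity subset is smaller and may be selected by health: at mean 0.4 and SD 0.5, power is 75% with 13 patients, 62% with 10 and 56% with 9. It is therefore supportive only. Dosing is unchanged.
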